# **15.6 Interim Analyses**

Considering the objectives and nature of this Master Protocol, collecting safety, tolerability, and feasibility data for the full duration of each RSSP as well as the wide spectrum of exploratory endpoints are essentially important for the RSSP objectives. As such, no interim efficacy or futility analyses will be conducted.

## **15.7 Secondary Endpoints**

#### 15.7.1 Feasibility

No formal analyses are specified for this secondary objective. However, key feasibility metrics such as enrollment timelines, retention, visit compliance, etc. will be tracked throughout each RSSP.

#### 15.7.2 Safety

Analyses to examine safety of each active treatment versus placebo will involve comparisons of the percentage of participants within each RSSP reporting at least one treatment-emergent AE during the RSSP. This will be assessed via either chi-square tests of logistic regression models. Analyses will be repeated to compare the frequency of AEs within each MedDRA system organ class (SOC). If there are significant differences between groups within any specific SOC, then additional tests will compare differences across groups for specific MedDRA preferred terms in order to further explore the cause of the observed difference. SAEs will be analyzed in the same manner as described above. Additional analyses will assess treatment-related SAEs and unanticipated SAEs in a comparable manner.

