- 2. After confirming any additional regimen specific eligibility requirements, participants will be stratified by MDS-UPDRS Part III score at baseline ( $<7 \text{ vs.} \ge 7$ ). Within the corresponding strata, each participant will be randomized in a *J*:1 manner to either active treatment or placebo, where *J* (<K) is the number of enrolling regimens for which the participant was eligible at the time of randomization.

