### 8.2 Randomization

#### 8.2.1 Randomization Procedures

Randomization will be conducted using an interactive response technology (IRT) system embedded within the EDC. The randomization for the Master Protocol consists of a two-stage tiered randomization as described below (see Figure 1).

- 1. In the first stage, participants will initially be assessed according to the Master Protocol inclusion and exclusion criteria. All eligible participants will then be assessed for any additional RSSP specific inclusion and exclusion criteria above that for the Master Protocol that are accessible at the time of screening. Assuming a research participant qualifies for one or more of the ongoing RSSPs, the participant will be randomized equally among all *J* actively enrolling regimens for which they are eligible. Here, regimen denotes both active treatment and placebo groups.
- 2. In the second stage, once assigned to a regimen the participant will then provide informed consent for that specific regimen at their scheduled Regimen-Specific Screening visit. If all additional regimen specific eligibility criteria are met, participants will be stratified by

their baseline MDS-UPDRS part III score ( $<7 \text{ vs.} \ge 7$ ) and randomized in a *J*:1 manner via the IRT system to either the active treatment or placebo for the sub protocol. If the participant screen fails for the assigned regimen (prior to randomization within the regimen), they can be re-randomized to one of the other actively enrolling regimens and complete the required screening procedures. Eligible participants who choose not to consent to their assigned regimen will not be given the opportunity to be re-randomized into an alternative regimen.

The objective of the randomization scheme is to have approximately 1:1 randomization for each active treatment versus concurrently randomized controls.

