# **15. STATISTICS**

### **15.1 Primary Endpoints and Analyses**

**Primary scientific question:** Does the treatment slow the rate of progression in DAT SPECT mean striatum SBR or MDS-UPDRS Part III score for those with NSD Stage 2B?

**Primary Endpoints.** To explore this question from the perspective of a biomarker and a clinical measure of symptom worsening, there are two primary endpoints: (a) DAT SPECT mean striatum SBR across time and (b) MDS-UPDRS Part III score across time. Both endpoints are measured until the final participant randomized has the opportunity to complete their 24 month follow up visit in the assigned RSSP. This results in greater than 24 months of follow up on participants randomized earlier in enrollment.

**Primary Analyses.** The Bayesian primary analysis models estimate a difference in the rate of change of each primary endpoint from baseline through last visit, comparing active treatment versus a shared concurrent and non-concurrent placebo. Analyses of treatment superiority will be performed assuming one-sided type I error of 5%. Each primary endpoint will be tested with equal priority with respect to active treatment superiority versus shared concurrent and non-concurrent placebo.

1) DAT SPECT Mean Striatum SBR. A Bayesian repeated measures model of mean striatum SBR, adjusted for baseline MDS-UPDRS part III score strata, will be used to compare the slope of active treatment versus the shared concurrent and non-concurrent placebo arm. The model allows for heterogeneity across individual baseline mean striatum SBR values and individual slopes, heterogeneity across regimens due to minor differences in the inclusion/exclusion criteria or mode of administration.

It is hypothesized that an effective treatment will decrease the progression rate and slow the decline in mean striatum SBR. A greater negative slope indicates a greater reduction in the biomarker and a greater progression rate. The following hypothesis test for a difference in slopes between active treatment and placebo groups will be conducted using the Bayesian posterior distribution.

H0: The active treatment group's average mean striatum SBR slope is equal to or less than that of the shared placebo arm.

 $\mathrm{H}_{a}\!\!:$  The active treatment group's average mean striatum SBR slope is greater than that of the shared placebo arm

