#### 15.7.3 Tolerability

The assessment of tolerability will examine the percentage of participants on each treatment group (within each RSSP) who complete the full RSSP on their initially actively assigned treatment regimen. Participants who withdraw from treatment early will be counted as having not tolerated treatment, whether the withdrawal was due to an AE or not. The percentage meeting the tolerability definition within each group will be assessed via chi-square tests or logistic regression models.

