### **16.3 Participant Information & Informed Consent**

This Master Protocol will be conducted in compliance with Title 21 Part 50 of the United States of America CFR, Federal Regulations and ICH Guidance Documents pertaining to informed consent.

At the first visit, prior to initiation of any Master Protocol-related procedures, participants will be informed about the nature and purpose of the MP, participation/termination conditions, and risks and benefits. Participants will be given adequate time to ask questions and become familiar with the Master Protocol prior to providing consent to participate. Participants will give their documented informed consent to participate in the Master Protocol and will be provided with a copy of the fully executed Master Protocol consent form for their records. Participants meeting Master Protocol eligibility criteria will be randomly assigned to an actively enrolling RSSP.

Participants will then be informed about the intervention specific to their assigned RSSP and any participation/termination conditions or risks and benefits specific to that regimen as per RSSP protocol. Participants meeting additional eligibility criteria required by their assigned RSSP, if any, will be randomized in a K:1 ratio to receive either active treatment or matching placebo in that sub-protocol.

In some situations, an individual may be re-assigned to multiple different regimens, if eligible. The procedures detailing the re-assignment process can be found in Section 8.4 Screen Failures and Reassignment.

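### If J varies within an RSSP, the pooled safety and tolerability percentages can be confounded; the comparison should be stratified by J

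*Protocol*

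**What the plan says.** **Endpoints and tests.** Section 15.7.2 (Safety) specifies "comparisons of the percentage of participants within each RSSP reporting at least one treatment-emergent AE during the RSSP" and then states: "This will be assessed via either chi-square tests of logistic regression models" (the *of* is presumably *or*). SAEs are handled in the same way. Section 15.7.3 (Tolerability) takes the percentage of participants "who complete the full RSSP on their initially actively assigned treatment regimen", which "will be assessed via chi-square tests or logistic regression models". Neither section names a stratum, a covariate or an exposure term.

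**Allocation.** Sections 5.5, 8.2.1 and 15.2 and the Randomization paragraph of the Synopsis give a J:1 ratio of active to placebo within the assigned regimen. The Synopsis says that J "is the number of enrolling regimens for which the participant was eligible at the time of randomization". The only stratification factor at this step is baseline MDS-UPDRS Part III (below 7 versus 7 or more). Section 8.2.1 gives the aim: "The objective of the randomization scheme is to have approximately 1:1 randomization for each active treatment versus concurrently randomized controls". Section 16.3 differs on the ratio: participants "will be randomized in a K:1 ratio to receive either active treatment or matching placebo in that sub-protocol".

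**Follow-up.** Participants stay in the RSSP until the last one randomized has had the chance to reach 24 months. Section 15.1 notes: "This results in greater than 24 months of follow up on participants randomized earlier in enrollment".

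**The concern.** J belongs to the participant and the date, not to the RSSP. The platform is perpetual, regimens may enter at any time without limit, and each closes to enrolment at its target. Even with a fixed set of open regimens, J depends on how many of them a person qualifies for.

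A participant with J = 1 has a 50% chance of placebo; one with J = 3 has a 25% chance. When such participants are pooled within one RSSP, placebo over-represents those with low J. Two features linked to outcome can follow J:

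- **Enrolment time.** Early enrollees are observed for longer, so they have more time to report an AE or to stop treatment.
- **Eligibility profile.** Qualifying for fewer regimens may go with different health.

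A test on pooled percentages then compares arms with different mixes. It could show a safety or tolerability difference when the drug has none, or mask a real one.

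**Working it through.** **1. The protocol's allocation aim.** With J eligible regimens, the chance of one particular active arm is (1/J) × J/(J+1) = 1/(J+1). The chance of placebo in any regimen is also 1/(J+1). The stated aim of about 1:1 against concurrent placebo is therefore reproduced for every J. Inside one RSSP the ratio is J:1, so 125 active participants go with 125, 62.5 or 41.7 placebo participants for J = 1, 2 or 3.

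**2. Assumptions for the bias calculation.** The protocol gives no enrolment duration, J path or event rate, so these are assumed. Enrolment is uniform over E months, with equal numbers in each half. J changes at E/2. Follow-up is 24 months plus the enrolment time remaining. The event hazard h is constant and identical in both arms, so the true effect is zero.

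**3. One case in full: E = 24, J from 1 to 3, h = 0.10 per year.** Take 100 participants per half: 50 active and 50 placebo in the first, 75 and 25 in the second. Follow-up runs from 36 to 48 months in the first half (mean 42) and from 24 to 36 in the second (mean 30).

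- Mean follow-up, active: (50×42 + 75×30)/125 = 34.8 months.
- Mean follow-up, placebo: (50×42 + 25×30)/75 = 38.0 months.
- First-half risk, either arm: 1 − (e^−0.3 − e^−0.4)/0.1 = 0.295.
- Second-half risk, either arm: 1 − (e^−0.2 − e^−0.3)/0.1 = 0.221.
- Active: (50×0.295 + 75×0.221)/125 = 25.1%.
- Placebo: (50×0.295 + 25×0.221)/75 = 27.0%.

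The difference is −2.0 points before rounding of the two percentages. Within each half it is exactly zero, so stratifying by J removes it.

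**4. Range.** Active minus placebo, in percentage points, with no true effect:

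| J path | Enrolment (months) | h = 0.05 | 0.10 | 0.20 | 0.80 |
|---|---|---|---|---|---|
| constant (1 or 2) | 12, 24 or 36 | 0.0 | 0.0 | 0.0 | 0.0 |
| 1 to 2 | 12 | −0.4 | −0.7 | −1.0 | −0.9 |
| 1 to 2 | 24 | −0.7 | −1.3 | −1.9 | −1.3 |
| 1 to 2 | 36 | −1.1 | −1.8 | −2.6 | −1.4 |
| 1 to 3 | 12 | −0.6 | −1.0 | −1.6 | −1.5 |
| 1 to 3 | 24 | −1.1 | −2.0 | −2.9 | −2.0 |
| 1 to 3 | 36 | −1.7 | −2.8 | −4.0 | −2.2 |

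Of the 24 cells with varying J, 19 are at least 1 point in size. If J goes from 3 to 1, the sizes equal those of the 1-to-3 rows and the signs are positive. With 125 active participants, the type I error of a two-sided 5% chi-square test (normal approximation) ranges from 5.1% to 8.7%. The top value needs J from 1 to 3 and 36 months of enrolment.

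**5. Tolerability.** Read h = 0.10 as the discontinuation hazard, with J from 1 to 3 and E = 36. Completion is then 100 − 28.2 = 71.8% on active and 100 − 31.0 = 69.0% on placebo, with no true difference.

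**6. Eligibility route, equal follow-up.** Suppose half the RSSP has J = 1 and AE risk 25%, and half has J = 3 and risk 15% (assumed). Active: (50×0.25 + 75×0.15)/125 = 19.0%. Placebo: (50×0.25 + 25×0.15)/75 = 21.7%. The difference is −2.7 points. If the two risks are equal, it is zero.

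**The case against.** **J may not vary.** The protocol allows regimens to be added but does not say that J will change during any particular RSSP. With constant J, the arms are randomized over the same period and from the same population, and the bias is zero. This stands, and it makes the point conditional. A reader might infer that the contrast *is* confounded as designed; the documents do not support that.

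**Unequal follow-up alone is harmless.** A reader might also infer that follow-up beyond 24 months biases the comparison by itself. At fixed J it affects both arms alike.

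**Logistic regression is also named.** Its covariates may properly be left to the SAP. This stands too, so the absence of a covariate list is not the complaint. What remains is that the protocol expressly permits an unadjusted chi-square test. By contrast, the exploratory analysis in Section 15.8.1 uses censoring and a stratified log-rank test.

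**The consequences are limited.** RSSP success rests on the two primary endpoints only, and no decision rule is tied to these tests. Under Section 14.8 the DSMB also sees the intervention against all concurrent placebo, where allocation is 1:1 at each J. Section 15.1 describes differences between regimens' eligibility criteria as minor, which weakens the eligibility route.

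**Cutting tolerability at Month 24 would be a different endpoint.** The varying completion target might suggest such a redefinition. But Section 6.2 declares completion of the RSSP as the endpoint, and Section 15.6 stresses data over its full duration. The varying target creates no between-arm bias unless J varies, and stratifying by J then deals with it.

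**Conclusion.** The point holds conditionally. When J varies among participants in the same RSSP, the pooled percentages in Sections 15.7.2 and 15.7.3 compare arms with different enrolment-time and eligibility mixes, and the permitted chi-square test does not correct for this. When J is constant there is no bias.

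The size is modest: 0.4 to 4.0 percentage points in the enrolment-time scenarios, mostly 1 to 4, and 2.7 points in the eligibility example. The direction depends on whether J rises or falls. All these figures rest on assumed J paths, enrolment periods and event rates, and on everyone being observed until the RSSP closes. They show what the method can produce, not what will happen in a given regimen. The change is still worth making, because it is cheap and removes both routes of bias.

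The conflict between K:1 in Section 16.3 and J:1 in the Synopsis and Sections 5.5, 8.2.1 and 15.2 is real but separate. K is the number of actively enrolling regimens, so the two ratios differ whenever someone is not eligible for all of them. It adds nothing to the confounding argument.

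**What to change.** - In Sections 15.7.2 and 15.7.3, replace the unadjusted chi-square option with an analysis stratified by J at randomization: Cochran-Mantel-Haenszel, or logistic regression with J as a factor. Given J, allocation within the RSSP depends on neither enrolment time nor eligibility, so this covers both routes.
- Add exposure-adjusted AE and SAE rates as a supplement to the percentages.
- Keep the full-RSSP definition of tolerability.
- Separately, reconcile the ratio in Section 16.3 with the Synopsis and Sections 5.5, 8.2.1 and 15.2.

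The cost is wording and a little more analysis. J must already be known to the randomization system to apply the ratio, so no new data are needed. The drawback is small strata if some values of J are rare; a rule for combining sparse strata should then be fixed before unblinding.

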# 5.6 Number of Planned Participants and Treatment Arms

The sample size for each regimen is approximately 125 participants on active treatment and at least 125 corresponding shared concurrent and non-concurrent placebo participants. In this trial, multiple investigational therapeutic products for NSD Stage 2B will be tested simultaneously or sequentially. These investigational products will be provided by different partners, including pharmaceutical companies or academic groups.

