# 14.7 Independent Medical Monitor (IMM)

At least one IMM will be appointed for this Master Protocol. The IMM will review all reported SAEs, AEs deemed to be severe, and AEs deemed to be treatment-related by the site in near realtime in order to evaluate them to identify the need for expedited reporting. For any such reported SAEs or AEs, the IMM will be notified to prompt a review of the event for seriousness, causality, expectedness, and additional factors which may affect reporting responsibilities. The IMM will review the SAE within 24 hours of receipt notification. If additional information is required to complete the evaluation of an SAE, the IMM may contact the MM to request more information from the site.

The unblinded statistician will provide aggregate reports of all AEs to the IMM for review on a quarterly basis (or as specified in each RSSP). These aggregate reports will summarize all AEs by severity (serious/not serious), attribution (anticipated or unanticipated), and relationship to the regimen-specific treatment. All AEs will be coded using the Medical Dictionary for Regulatory Activities (MedDRA: version 26.1). The IMM will review these quarterly reports for any trends of interest or safety signals. Should any concerns arise due to observed trends, the IMM may send a written recommendation to the unblinded statistician via email requesting that the report be forwarded to the Data and Safety Monitoring Board (DSMB) for future review, as appropriate.

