## **15.2 Randomization**

The platform trial incorporates two stages of randomization.

- 1) Equal randomization to all currently *J* actively enrolling regimens for which a participant is eligible, where regimen denotes both active treatment and placebo groups.
- 2) After confirming any additional regimen specific eligibility criteria are met, stratification by baseline MDS-UPDRS part III score (<7 vs.  $\geq$ 7), and then *J*:1 randomization within assigned regimen to either active treatment or placebo.

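### Section 15.7.2 compares preferred terms only after a significant organ-class test, so an excess confined to one event can be diluted and left uncompared in the RSSP safety analysis

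*Protocol*

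**What the plan says.** Protocol section 15.7.2 analyses safety in steps. It starts with "comparisons of the percentage of participants within each RSSP reporting at least one treatment-emergent AE during the RSSP". It names the method as follows: "This will be assessed via either chi-square tests of logistic regression models" (the "of" is presumably a slip for an alternative between the two). The analysis is then repeated for each MedDRA system organ class. The third step is conditional: "If there are significant differences between groups within any specific SOC, then additional tests will compare differences across groups for specific MedDRA preferred terms", and its stated purpose is to explain the class difference already seen. For serious events, "SAEs will be analyzed in the same manner as described above", and treatment-related and unanticipated SAEs are handled comparably.

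No other section provides a between-arm comparison by preferred term that does not depend on the class result. The Protocol states neither a significance level nor expected event rates for these tests.

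**The concern.** The class-level test asks whether the share of participants with any event in an organ class differs between arms. If a drug raises one preferred term only, every unrelated event in that class adds noise and hides some of the excess, because participants who would have had another event in the class anyway cannot be counted a second time. The result that decides whether the term is examined is therefore less sensitive than an examination of the term itself.

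Safety is a secondary endpoint of every RSSP (section 6.2), and the platform is a phase 2A proof-of-concept trial. At this stage an unexpected, event-specific signal is one of the main things a safety analysis should be able to show. Requiring class significance first guards against false alarms at the cost of missed signals, and in early safety review a missed signal is usually the worse error. Because the text sits in the Master Protocol, every RSSP inherits it.

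**Working it through.** The plan has no figure of its own to reproduce, so the check measures what the condition costs.

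**Inputs from the Protocol**
- Size: "approximately 125 participants on active treatment and at least 125 corresponding shared concurrent and non-concurrent placebo participants" (section 5.6).
- Allocation: J:1 "randomization within assigned regimen to either active treatment or placebo" (section 15.2). Section 15.7.2 compares within each RSSP, so with 125 on active treatment the RSSP's own placebo group is 125/J: 125 for J=1 and about 62 for J=2.
- Test: chi-square (section 15.7.2).

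**Assumptions, not in the Protocol**
- Two-sided 5% level and no continuity correction.
- Class frequency is the percentage of participants with at least one event in the class.
- The drug affects one term only. All other terms in the class together have the same background rate b in both arms, independent of the affected term.
- Main case: affected term at 8% active v 1% placebo.

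**Dilution**

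Class rate in an arm = 1 − (1 − b)(1 − p), where p is the rate of the affected term. The class difference is therefore (1 − b) × (difference in p).

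At b = 25%, 125 v 125:
- Class rates: active 1 − 0.75 × 0.92 = 31.0%; placebo 1 − 0.75 × 0.99 = 25.75%; difference 5.25 points.
- Class standard error (pooled rate 28.375%): √(0.28375 × 0.71625 × 2/125) = 0.0570, so the expected z is 0.0525/0.0570 = 0.92.
- Term itself (pooled rate 4.5%): √(0.045 × 0.955 × 2/125) = 0.0262, so the expected z is 0.07/0.0262 = 2.67.

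The same excess is well above the 1.96 threshold at term level and well below it at class level. The smaller difference matters less than the larger variance that the background adds.

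**Simulation**

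The normal approximation is rough at a 1% rate, so the probabilities come from simulation (400,000 trials per case, both tests on the same participants). The conditional procedure succeeds only if both the class test and the term test are significant.

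| Background b | Class test significant | Conditional procedure finds the term | Direct comparison finds the term |
|---|---|---|---|
| 2% | 62% | 59% | 81% |
| 5% | 45% | 43% | 81% |
| 15% | 22% | 21% | 81% |
| 25% | 15% | 14% | 81% |
| 35% | 11% to 12% | 10% | 81% |

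(8% v 1%, 125 v 125.)

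**Other cases**
- J=2 (125 v 62), 8% v 1%, b = 25%: conditional 8%, direct 53%.
- 12% v 2%, 125 v 125: conditional 65% at b = 5% and 15% at b = 40%; direct 91%.
- 15% v 2%, b = 5%, 125 v 125: class test significant in 84%.
- 20% v 5%, b = 5%, 125 v 125: class test significant in 86%.
- 20% v 2%, b = 10%, 125 v 125: class test significant in 90%.
- 25% v 2%, b = 25%, 125 v 125: class test significant in 82%.

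**The case against.** A reader might infer that a clear drug-specific event will usually never be tested. The documents do not support that. They give no event rates, class backgrounds or significance level, and the answer depends on all three. For large excesses the class test usually succeeds (82% to 90% in the cases above), and even 8% v 1% passes in 62% of trials if the class background is only 2%. This objection stands and limits the claim.

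A reader might also infer that the rule hides signals altogether. It does not. The independent medical monitor reviews all SAEs, severe AEs and AEs judged treatment-related in near real time and receives aggregate reports each quarter: "The IMM will review these quarterly reports for any trends of interest or safety signals" (section 14.7). The DSMB should examine a notable rise in any AE (section 14.8). Events of special interest are defined in each RSSP (section 14.4), and RSSPs may add AE reporting and stopping rules (section 14.5). None of these depends on a class test. But they are monitoring during conduct, not the reported analysis of the secondary safety endpoint. Section 14.7 describes summaries by seriousness, attribution and relationship and names no comparison of arms by preferred term. Events of special interest have to be named in advance, so they cannot catch the unexpected one.

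Two further points have some weight. Testing the class before the term is a recognisable way to limit multiplicity, and dropping it will produce more chance differences. The 81% also belongs to a favourable case: it needs J=1 and the uncorrected test. With Fisher's exact test at 125 v 125 it is about 71%, and at J=2 the uncorrected test gives 53%. The conditional procedure falls further still at J=2, so the comparison keeps its direction.

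Lastly, descriptive tables by preferred term are commonly left to the SAP, which is not at hand. Their absence from the Protocol is not the complaint. The complaint is the condition that the Protocol does state.

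**Conclusion.** The point holds in a limited form. Section 15.7.2 fixes a rule under which the formal comparison of preferred terms, for AEs and SAEs alike, depends on a significant class test. Followed as written, it can leave an excess in one term without any comparison in the RSSP safety analysis.

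Under the stated assumptions the loss is large for a moderate excess in a class with appreciable background: 14% against 81% for 8% v 1% at 25% background. It is smaller in a quiet class (59% against 81% at 2% background) and slight for large excesses. Participants are 60 or older and treated for at least 24 months (sections 7.1 and 5.9), so appreciable background in common classes is plausible, but the Protocol gives no figure for it. Every percentage here rests on the assumed rates, the 5% level, the uncorrected test and independent background. The existence of the rule does not. It deserves correction because the change is cheap and monitoring covers the gap only in part.

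**What to change.** In section 15.7.2, delete the requirement that the class differ significantly before preferred terms are compared. State instead that counts, the risk difference and its 95% confidence interval will be given by arm for every preferred term at or above a prespecified frequency in either arm (for example 3%), and for all SAEs and AESIs, whatever the class result and labelled as descriptive. The class-level tests can stay. If the SAP already contains such tables, the Protocol wording should be brought into line with it.

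The cost is one edit to Master Protocol text, which then applies to every RSSP, and longer tables. No visits, participants or efficacy type I error are affected. The downside is more comparisons and so more chance differences; the descriptive label and the frequency cut-off keep these in proportion.
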